Anticoagulants, oral (warfarin)	Potential increased warfarin metabolism ¹	Adjustment of warfarin dosage may be needed ¹
Anticonvulsants (phenytoin)	Potential increased phenytoin metabolism ¹	Adjustment of phenytoin dosage may be needed ¹
Antifungals, azoles (fluconazole, itraconazole, ketoconazole)	Potential increased metabolism of the antifungal ¹	Adjustment of antifungal dosage may be needed ¹
Antiretrovirals, HIV entry inhibitors		Maraviroc: Concomitant use not recommended
Antiretrovirals, HIV protease inhibitors (PIs)	Indinavir: Decreased AUC and concentrations of indinavir; no effect on pharmacokinetics of rifapentine ¹ Atazanavir, fosamprenavir, lopinavir, nelfinavir, ritonavir, saquinavir: Potential decreased concentrations of the PI ¹	Concomitant use with PIs not recommended ^{1,14 a} Manufacturer of rifapentine states use with extreme caution, if at all, in patients receiving PIs ¹
Antiretrovirals, nonnucleoside reverse transcriptase inhibitors (NNRTIs)	Delavirdine: Potential increased metabolism of the NNRTI ¹ Delavirdine, nevirapine: HIV-infected patients receiving a NNRTI who are receiving rifapentine for TB may have a higher rate of TB relapse than those treated with other rifamycin-based regimens	Concomitant use with NNRTIs, with the exception of efavirenz, is not recommended ^{14 a}
Barbiturates	Potential increased metabolism of the barbiturate ¹	Adjustment of barbiturate dosage may be needed ¹
Benzodiazepines (e.g., diazepam)	Potential increased metabolism of the benzodiazepine ¹	Dosage adjustment of the benzodiazepine may be needed ¹
Calcium-channel blocking agents (diltiazem, nifedipine, verapamil)	Potential increased metabolism of the calcium-channel blocking agent ¹	Dosage adjustment of the calcium-channel blocking agent may be needed ¹
Cardiac glycosides	Potential increased metabolism of the cardiac glycoside ¹	Dosage adjustment of the

Interactions

		cardiac glycoside may be needed ¹
Chloramphenicol	Potential increased metabolism of chloramphenicol ¹	Dosage adjustment of chloramphenicol may be needed ¹
Clofibrate	Potential increased metabolism of clofibrate ¹	Dosage adjustment of clofibrate may be needed ¹
Corticosteroids	Potential increased metabolism of the corticosteroid ¹	Dosage adjustment of the corticosteroid may be needed ¹
Dapsone	Potential increased metabolism of dapsone ¹	Dosage adjustment of dapsone may be needed ¹
Doxycycline	Potential increased metabolism of doxycycline ¹	Dosage adjustment of doxycycline may be needed ¹
Erlotinib	Possible decreased erlotinib AUC ^b	Avoid concomitant use if possible ^b
Fluoroquinolones (e.g., ciprofloxacin)	Potential increased metabolism of ciprofloxacin ¹	Dosage adjustment of the fluoroquinolone may be needed ¹
Estrogens/Progestins	Hormonal contraceptives (oral or other systemic): Potential interaction with oral or other systemic hormonal contraceptives ¹	Use nonhormonal methods of contraception ¹
Immunosuppressive agents (cyclosporine, tacrolimus)	Potential increased metabolism of the immunosuppressive agent ¹	Dosage adjustment of the immunosuppressive agent may be needed ¹
Levothyroxine	Potential increased levothyroxine metabolism ¹	Dosage adjustment of levothyroxine may be needed ¹
Macrolides (clarithromycin)	Potential increased clarithromycin metabolism ¹	Dosage adjustment of clarithromycin may be needed ¹
Opiate agonists (methadone)	Potential increased metabolism of methadone ¹	Dosage adjustment of methadone may be needed ¹
Psychotherapeutic agents (amitriptyline, haloperidol, nortriptyline)	Potential increased metabolism of the psychotherapeutic agent ¹	Dosage adjustment of the psychotherapeutic agent may be needed ¹
Quinine	Potential increased metabolism of quinine ¹	Dosage adjustment of quinine may be needed ¹
Sildenafil	Potential increased sildenafil metabolism ¹	Dosage adjustment of sildenafil may be needed ¹
Sulfonylurea antidiabetic agents	Potential increased metabolism of the sulfonylurea agent ¹	Dosage adjustment of the antidiabetic agent may be needed ¹
Theophylline	Potential increased metabolism of theophylline ¹	Dosage adjustment of theophylline may be needed ¹
Tests for serum folate	Standard microbiologic assays for serum folate and	Consider using alternative

and vitamin B ₁₂	vitamin B ₁₂ are inhibited by therapeutic rifampin concentrations; similar effects may occur with rifapentine ¹	assays to determine serum folate and vitamin B ₁₂ ¹
-----------------------------	---	---

Concomitant use with HIV protease inhibitors (PIs) or certain HIV entry inhibitors not recommended unless there are no other choices because rifapentine decreases the therapeutic levels of these medications. Recent data by our group shows that it can be safely administered with efavirenz, the most commonly prescribed ART as first line therapy in Malaysia.

General Precautions

Discoloration of Body Tissues or Fluids

Urine, sweat, sputum, tears, and breast milk may have a red-orange coloration during rifapentine therapy. Soft contact lenses and dentures may become permanently stained. Prisoners in Malaysia do not have access to contact lens or dentures.

Patient Monitoring

In order to avoid excess hepatotoxicity, LFTs will be monitored at baseline.

Specific Populations

Pregnancy and Lactating

Rifapentine is Category C so pregnant and breast-feeding women will be excluded from treatment. Specifically, Rifampin administration during the last few weeks of pregnancy can cause postnatal hemorrhages in the mother and infant that require treatment with vitamin K. Similar effects may occur with rifapentine; appropriate clotting parameters should be evaluated if use of rifapentine is considered necessary during the last few weeks of pregnancy.

Specific Drugs and Laboratory Tests that can be affected by Rifapentine

ISONIAZID

Isoniazid (INH) is the recommended treatment for LTBI by the WHO and CDC and is one of the commonly used medications worldwide. Severe and rarely fatal hepatitis associated with INH therapy has been reported and may occur or may develop even after many months of treatment. The risk of developing hepatitis is age related and increased duration of treatment. Approximate case rates by age are: less than 1 per 1,000 for persons under 20 years of age, 3 per 1,000 for persons in the 20 to 34 year age group, 12 per 1,000 for persons in the 35 to 49 year age group, 23 per 1,000 for persons in the 50 to 64 year age group, and 8 per 1,000 for persons over 65 years of age. The risk of hepatitis is increased with daily consumption of alcohol (alcohol is NOT available to Malaysian prisoners). Precise data to provide a fatality rate for isoniazid-related hepatitis is not available; however, in a U.S. Public Health Service Surveillance Study of 13,838 persons taking isoniazid, there were 8 deaths (0.058% or 0.58 cases per 100,000) among 174 cases of hepatitis (0.012% or 126 cases per 100,000). Thus, drug-induced hepatitis is uncommon and mortality is rare.

Therefore, patients given INH should be carefully monitored and interviewed at monthly intervals. For persons 35 and older, in addition to monthly symptom reviews, hepatic enzymes

(specifically, AST and ALT (formerly SGOT and SGPT, respectively)) should be measured prior to starting isoniazid therapy and periodically throughout treatment. Usually, enzyme levels return to normal despite continuance of medication, but in some cases progressive liver dysfunction occurs. Other factors associated with an increased risk of hepatitis include daily use of alcohol, chronic liver disease and injection drug use. A recent report suggests an increased risk of fatal hepatitis associated with isoniazid among women, particularly black and Hispanic women. No blacks or Hispanics will be enrolled. More careful monitoring should be considered in these groups, possibly as frequently as monthly. If abnormalities of liver function exceed five times the upper limit of normal, discontinuation of INH should be strongly considered. Liver function tests are not a substitute for a clinical evaluation at monthly intervals or for the prompt assessment of signs or symptoms of adverse reactions occurring between regularly scheduled evaluations. Patients should be instructed to immediately report signs or symptoms consistent with liver damage or other adverse effects. These include any of the following: unexplained anorexia, nausea, vomiting, dark urine, icterus, rash, persistent paresthesias of the hands and feet, persistent fatigue, weakness or fever of greater than 3 days duration and/or abdominal tenderness, especially right upper quadrant discomfort. If these symptoms appear or if signs suggestive of hepatic damage are detected, isoniazid should be discontinued promptly, since continued use of the drug in these cases has been reported to cause a more severe form of liver damage.

Other side effects of INH include minimal drug interactions (none expected with these study participants ... eg, some antiseizure medications), peripheral neuropathy (obviated because we provide pyridoxine), and there are no drug interactions with HIV medications.

Methadone: Methadone is the current standard of care for treating opioid use disorders in Malaysia, and will be provided as part of routine clinical care. The most concerning problem that we are likely to encounter is drug interactions with either TB medication (specifically rifampin) or HIV medications (for which there are many). All patients initiating TB or HIV medications AFTER being stabilized on MMT will be monitored daily for two weeks for symptoms of opioid withdrawal using the Clinical Opioid Withdrawal Scale (COWS). We anticipate, however, that most patients will start their TB medications before receiving OAT and precipitating withdrawal symptoms will be unlikely. For those already on OAT, MMT doses will be increased by 5mg per day for mild symptoms, 10 mg per day for moderate symptoms and 20 mg per day for severe withdrawal using the Clinical Opioid Withdrawal Scale (COWS).

Buprenorphine/Naloxone (BPN/NLX): BPN/NLX, also known by the name SUBOXONE, consists of a mixed medication of buprenorphine (BPN) and naloxone (NLX) in a 4:1 ratio by mass, respectively. BPN is a μ -opioid receptor partial agonist, which functions by partially activating opioid receptors and imitating its effects; however, BPN's effect plateaus, thus giving the user only a minimal effect. NLX is a μ -opioid receptor antagonist with slightly lower affinity to opioid receptors than buprenorphine. When administered in combination with BPN, it aids in further reducing the partial agonist effect of BPN, especially when such is injected. Together, they ameliorate the euphoric and sedative effects of opioids by binding and blocking opioid receptors to reduce cravings by inducing a less intense receptor activation. BPN/NLX is FDA approved to treat opioid use and alcohol use disorders, and is available for use under the tongue or on the inside of the cheek. BPN/NLX has sometimes been a preferred mode of MAT as it has a reduced potential for diversion or abuse, can be taken home for daily self-administration and has shown increased engagement and retention in community-based treatment. (Malta, et al., 2019). Additionally, The buprenorphine/naloxone combination tablet (BPN/NLX) was

introduced in the Malaysian market in 2006 to reduce potential problems with diversion and abuse. When taken as directed, Naloxone does not interfere with Suboxone's primary ingredient, buprenorphine. The major ingredient in Suboxone, buprenorphine, has undergone in-depth studies since 1978, when it was originally introduced as a method of treating opiate addictions. Clinical trials sponsored by the National Institute on Drug Abuse have found buprenorphine to be effective in: alleviating withdrawal symptoms of opiate drugs, decreasing cravings, reducing illicit drug use, blocking the effects of other opiates, and retaining patients in treatment programs.

10. Minimizing Risks: Describe the manner in which the above-mentioned risks will be minimized.

Informed Consent: Informed consent will be obtained by the local RAs using an information sheet approved by the Medical Ethics Committee of the University of Malaya Medical Centre. Participants will also complete a standard consent form for the University of Malaya Medical Centre.

Face-to-Face Interviews and surveys/questionnaires: There are minimal risks expected from participating in interviews, such as feeling uncomfortable with certain topics being discussed. As mentioned previously, all participants for interviews will be reminded that their refusal to participate will in no way negatively affect their professional relationship with any of the participating agencies or clinics. If participants do feel uncomfortable about certain questions asked, subjects will be able to choose not to answer the question that makes them uncomfortable. All interviews and consultations will occur in private rooms, to ensure confidentiality. All data will be stored in secure locations. Everyone will be told that the meeting is confidential.

Recruitment: Recruitment procedures are designed to reduce the risk of confidentiality loss for participants. Patients will not be targeted for recruitment in this study. They will visit participating prisons for their routine medical care. They will be reassured that their participation is voluntary and confidential. For participants in Aim 1, recruitment will take place in a private prison room.

Monitoring Adverse Side Effects:

For patients in Aim 1, Part B (trial of 26H vs 12HR) and Part C (MMT, vs. no MAT), patients will be seen monthly clinically for symptoms of hepatitis or neuropathy and LFTs shall be monitored. Anyone whose LFTs increase to $>5X$ ULN, or $>3X$ ULN with symptoms of jaundice, nausea or fatigue, will be stopped from receiving medications and LFTs will be monitored weekly to ensure that LFTs are decreasing. Similarly, if patients develop Grade 3 or higher peripheral neuropathy, they will be discontinued. Of note, LFTs will be measured at baseline and monthly for 3 months for 12HR and monthly x 6 months for 26H.

MMT patients will be seen daily for the first month and may have their medications dispensed less frequently if they have no evidence of using illicit drugs by self-report or urine testing.

11. Data and Safety Monitoring Plan: Include an appropriate Data and Safety Monitoring Plan (DSMP) based on the investigator's risk assessment stated below. (Note: the HIC will make the final determination of the risk to subjects.) For more information, see the Instructions, page 24.

- a. What is the investigator's assessment of the overall risk level for subjects participating in this study?
- b. If children are involved, what is the investigator's assessment of the overall risk level for the children participating in this study?
- c. Include an appropriate Data and Safety Monitoring Plan. Examples of DSMPs are available here <http://www.yale.edu/hrpp/forms-templates/biomedical.html> for
 - i. Minimal risk
 - ii. Greater than minimal

Aim 1parts (a-c) requires a DSMB.

Data and Safety Monitoring Board

We will comprise a full Data and Safety Monitoring Board (DSMB), that will include three voting members from colleagues in the field. The PI on this grant is familiar with the implementation of a DSMB; he is currently serving as one of the board members of the NIDA Clinical Trials Network studies examining routine HIV testing among drug users.

The key elements of a DSMB include the following:

- 1) Selecting experts in the field (HIV, TB, Substance abuse) who will serve as members of the board. If funded, we will select two U.S. and one Malaysian experts to serve on the DSMB. As in other NIDA trials, we will work with NIDA staff to select these individuals. Individuals from NIDA will be responsible for the final invitation to participate on the Board. During the first six months of the study, while final implementation is being conducted, the DSMB will convene to go over their charge, examine the guidance set forth by the study team and to question the PI and biostatisticians about pre-defined endpoints. Once these outcomes and stopping rules are defined, the Board will reconvene at regularly scheduled times to assess outcomes.

Defining stopping rules. For Aim 1, part B, we will be examining completion and tolerability of two LTBI prevention strategies. The study is not powered to reduce development of active TB, but to establish safety in prisoners who have high prevalence of HCV infection. Tolerability (discontinuation from study medication) will be the primary outcome. All discontinuations will be reviewed by the PI and the team. Death will be brought to the DSMB within 24 hours if medication related (though most deaths are related to TB itself). If the discontinuation rate is 3-fold higher in either group, either in the interim analysis when 50% is enrolled or at any time within study assessment, the study will be stopped for safety purposes and a press release will be made. For Part B, we anticipate a difference between the control group and the two intervention groups of about 40%.

- 2)
- 3) Assessment of possible adverse consequences of the various interventions. No specific guidance is available for DSMBs for these kinds of interventions; however, we have considerable experience with CHRP, Project PLUS, Project TRUST, Project CONNECT, Project BEST and other community research studies to provide a specific plan. In fact, in order to collect information about the "safety" of the intervention, we intend to hire a research assistant to gather safety information from three independent sources. These include the weekly study meeting where all active participants are discussed, daily conversations with the Health Educators and weekly conversations with the subject

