in a 12HR combination since both isoniazid and rifapentine can damage the liver; CDC is calling for studies of 12HR in prisoners, but have not yet funded research. In the absence of studies of 12HR use in prisoners, it is crucial to assess both completion rates and tolerability (especially when high HCV prevalence is present).

Eligibility for Part B includes:

- 1) Meets inclusion criteria for Part A
- 2) Has latent TB (HIV+, or TST \geq 10mm (HIV-)) and no active TB disease
- 3) \geq 6 months before end of sentence to ensure option for treatment completion
- 4) AST/ALT <5 ULN, or AST/ALT <3 x ULN if TBil >2 x ULN
- 5) Not on a protease inhibitor (drug interaction with rifapentine)
- 6) No known porphyria
- 7) Not pregnant (women only).

Enrolled participants will undergo block stratified randomization, stratifying on four factors: a) CD4 <350 (if HIV+); b) HCV Ab status; c) ART status; and d) opioid dependence. After randomization and allocation to 12HR or 26H, participants will be provided 12HR weekly (12 weeks) and 26H daily (26 weeks) as directly observed therapy. Every 4 weeks, patients will be monitored for AST/ALT, adverse side effects and pregnancy. Premature treatment discontinuation will occur for any DAIDS Grade 4 toxicity, patient refusal to continue, or pregnancy (women only).

Study Design: TB Studies

Legend: LTBI=latent TB infection; H=isoniazid; HP=isoniazid + rifapentine; MMT= methadone maintenance treatment; BPN/NLX= buprenorphine/naloxone; OAT=opioid agonist treatment; ART= antiretroviral therapy; HCV= hepatitis C virus.

Part C:

A two-arm **preference trial** (no MAT, and methadone) of prisoners with opioid use disorders who are not or are currently being treated for TB and/or HIV, and are about to transition to the community and need to continue their treatment post-release. Patients may or may not be returning to Klang Valley and within 25 km of our research site. We anticipate enrolling 25-50 participants per arm.

Once consented, study participants will be provided an informed decision-making aid that will help them decide if medication-assisted treatment, specifically Methadone, is best for them. Participants will also have the option not to enroll in medication-assisted treatment.

[figure not shown]
Informed decision-making aid:

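### Part B bars protease inhibitors because of rifapentine, but not maraviroc or, with weaker support, NNRTIs other than efavirenz, which the protocol's own table also advises against

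*Combined protocol and SAP*

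**What the plan says.** Criterion 5 for Part B (Section V.3, Eligibility for Part B) reads "Not on a protease inhibitor (drug interaction with rifapentine"). The 1b list in Section V.7 repeats it. Neither list names another antiretroviral, and the separate exclusion paragraph in Section V.7 concerns pregnancy.

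The rifapentine interaction table in Section V.9 gives advice on three antiretroviral groups:

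- Protease inhibitors: not recommended, with the manufacturer's added advice to "use with extreme caution, if at all, in patients receiving PIs".
- Entry inhibitors: "Maraviroc: Concomitant use not recommended".
- NNRTIs: "Concomitant use with NNRTIs, with the exception of efavirenz, is not recommended".

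The paragraph after the table names protease inhibitors together with "certain HIV entry inhibitors not recommended unless there are no other choices because rifapentine decreases the therapeutic levels of these medications". It then says that efavirenz can be given safely and is the leading first-line antiretroviral in Malaysia. It does not repeat the caution on other NNRTIs.

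HIV-positive people on treatment can enter Part B, since the stratification factors include "HCV Ab status; c) ART status; and d) opioid dependence".

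**The concern.** Criterion 5 gives the rifapentine interaction as its reason, yet it covers one of the three antiretroviral groups that the protocol marks as not recommended on interaction grounds. A participant on maraviroc, or on an NNRTI such as nevirapine, meets every listed criterion and has an even chance of allocation to 12HR.

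For entry inhibitors the protocol names the harm: lower therapeutic levels of the HIV drug. What is at stake is therefore mainly the safety of HIV care in a few participants, not the validity of the comparison between arms.

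**Working it through.** The plan has no figure to reproduce here. The check sets the texts side by side and looks for another provision that would close the gap.

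**Step 1. Table against criterion.**

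| Group | Advice in Section V.9 table | Repeated in text after table | Barred in Part B lists |
|---|---|---|---|
| Protease inhibitors | Not recommended; extra manufacturer warning | Yes | Yes |
| Maraviroc | Not recommended | Yes, as certain entry inhibitors | No |
| NNRTIs except efavirenz | Not recommended | No | No |

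**Step 2. Strength of each gap.** For maraviroc, one sentence gives protease inhibitors and certain entry inhibitors the same recommendation, the same allowance where no alternative exists, and the same reason. The protocol turns the first half of that sentence into a bar and leaves the second half without a rule. The allowance cannot explain the difference, because it applies equally to protease inhibitors.

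For NNRTIs the support is weaker. The interaction column gives increased metabolism for delavirdine only. The other reason, attached to delavirdine and nevirapine, is that "HIV-infected patients receiving a NNRTI who are receiving rifapentine for TB may have a higher rate of TB relapse". Part B enrols people without active TB, so relapse does not carry over directly. The visible recommendation is not itself confined to TB disease. It does carry a footnote marker whose text is not in the document, so a limit stated there cannot be ruled out.

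**Step 3. Other safeguards.**

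- Section V.8 gives eligibility to research assistants using a REDCap form. The pre-enrolment tests it lists are liver function and pregnancy. Clinical judgement about whether an alternative drug exists is not built into that step.
- The TB specialist review in Section V.3, Part A, has the stated purpose of getting suspected TB treated.
- The Part B stop rule is "Premature treatment discontinuation will occur for any DAIDS Grade 4 toxicity, patient refusal to continue, or pregnancy (women only"). Section V.10 adds liver-enzyme and neuropathy thresholds. None of these concerns the antiretroviral regimen.

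The information needed is already collected in principle. Criterion 5 requires staff to know whether a protease inhibitor is being taken, and ART status is needed for stratification. Only the rule is missing.

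**Step 4. Possible size.** Section V.12 plans 177 per arm and 354 in total, so the share allocated to 12HR is 177/354 = 0.50. The documents do not give the ART mix, and Section V.3 lists the prison formulary among data that may still be collected. With an assumed share s of HIV-positive participants on one of these drugs, the number allocated to 12HR per 100 HIV-positive participants randomised is 100 × s × 0.50:

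- s = 0%: 0
- s = 2%: 1
- s = 5%: 2.5
- s = 10%: 5

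**The case against.** The strongest reply is that a caution in a risk table is not an eligibility rule. The table covers many drug groups. It also advises avoiding erlotinib where possible and using nonhormonal contraception, and neither became a criterion. Protease inhibitors carry the strongest antiretroviral wording, so barring only them could be deliberate. This has some force for NNRTIs. It does not explain the absence of any rule for maraviroc, which shares a sentence, a qualifier and a stated harm with protease inhibitors.

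A second reply is that nobody may be affected. Maraviroc is named only in its table row, and efavirenz, the permitted NNRTI, is the leading first-line drug. Nevirapine appears in Section V.11, but about methadone levels, which is not evidence of its use in Part B. This stands, and it is why the point is minor.

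Three stronger readings are tempting and are not supported:

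- A reader might infer that the criterion contradicts the table. It does not; it is narrower than the table.
- A reader might infer that non-efavirenz NNRTIs are shown to be harmful with weekly preventive dosing. The documents do not establish that.
- A reader might infer from the stop rules that ART started or changed during 12HR should trigger a matching on-treatment rule. The documents give no basis for choosing between barring the ART change, stopping 12HR and monitoring. Stopping 12HR would add discontinuations in one arm only, unrelated to tolerability. Section V.11 makes discontinuation the primary outcome, and Section V.12 compares completion.

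**Conclusion.** The concern holds as a minor gap between Part B eligibility and the protocol's own interaction advice. It is firm for maraviroc. For NNRTIs other than efavirenz it rests on the visible wording of one table row, with a rationale that fits TB treatment better than prevention. Someone who meets every criterion could be randomised to a combination the protocol advises against, and no other criterion, review step or stop rule prevents it.

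Confidence is high in the textual comparison. How many people it touches is unknown: the range of 0 to 5 per 100 HIV-positive participants randomised depends on an assumed 0% to 10% use of these drugs, for which the documents give no source. No sample-size or power figure changes.

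**What to change.** In both Part B lists (Sections V.3 and V.7) and in the REDCap eligibility form, extend criterion 5 to bar protease inhibitors, maraviroc and any NNRTI other than efavirenz, keeping the rifapentine interaction as the reason. If the clinical team judges non-efavirenz NNRTIs acceptable with weekly preventive dosing, add maraviroc only and state that reasoning in the protocol. The table row itself should stay as it is, because it carries a source citation and a footnote that cannot be seen here.

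The cost is one phrase in two lists and one form item. A few HIV-positive participants may become ineligible. They would be kept out of both arms, even though Section V.9 reports no interaction between isoniazid and HIV drugs; criterion 5 already imposes that cost on protease-inhibitor users. Because the rule acts before randomisation, it does not disturb the comparison between arms.

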Hepatic Effects: Hepatic inflammation has been described in patients taking Rifapentine. Rifapentine use in patients with abnormal liver function tests and/or liver disease should *be* when considered necessary (e.g., need for treatment of LTBI or active TB) and *only* with caution and close medical supervision. Supervision includes examining for hepatotoxicity while examining for jaundice. Rifapentine should be discontinued if signs of liver disease develop or worsen (AST or ALT $>5X$ ULN, or $>3X$ ULN with symptoms of jaundice, nausea or fatigue,). The risk is elevated if administered with other antituberculosis agents (e.g., isoniazid, pyrazinamide) if these drugs are used with rifapentine.¹

Hyperbilirubinemia (resulting from competition between rifapentine and bilirubin for excretory pathways in the liver) possible; such competition has been reported between rifampin and bilirubin. An isolated report of moderate increase in bilirubin and/or transaminase concentrations is not an indication to interrupt rifapentine therapy; the decision to discontinue therapy should be made after repeating the tests, noting trends in the concentrations, and considering the patient's clinical condition.

Clostridium difficile-associated Diarrhea and Colitis: Treatment with anti-infectives, including rifamycins, may permit overgrowth of clostridia though this is an extremely rare event. Consider *C. difficile*-associated diarrhea and *colitis* (CDAD; also known as antibiotic-associated diarrhea and colitis or pseudomembranous colitis) if diarrhea develops and manage accordingly with examination of stool and possibly starting empiric metronidazole. Some mild cases of CDAD may respond to discontinuance alone. Manage moderate to severe cases with fluid, electrolyte, and protein supplements; appropriate anti-infective therapy (e.g., oral metronidazole or vancomycin) recommended if colitis is severe.¹ Agents inhibiting peristalsis contraindicated in these patients.

Drug or Test	Interaction	Comments
β-Adrenergic blocking agents	Potential increased metabolism of the β-adrenergic blocking agent ¹	Dosage adjustment of the β-adrenergic blocking agent may be needed ¹
Antacids		In clinical studies, patients were advised to take rifapentine 1 hour before or 2 hours after antacids ¹
Antiarrhythmic agents (disopyramide, mexiletine, quinidine, tocainide)	Potential increased metabolism of the antiarrhythmic agent ¹	Dosage adjustment of the antiarrhythmic agent may be needed ¹

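### Part B states two different mandatory rules for stopping study drug in a participant, with no order of precedence, although drug discontinuation is named as the primary outcome and drives the trial-stopping trigger

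*Combined protocol and SAP*

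**What the plan says.** **Research plan, Part B (Section V, item 3).** After describing observed dosing and four-weekly checks, the plan states: "Premature treatment discontinuation will occur for any DAIDS Grade 4 toxicity, patient refusal to continue, or pregnancy (women only". It gives no ULN multiple and no separate grade for neuropathy.

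**Monitoring of adverse effects (Section V, item 10).** The scope is explicit: "For patients in Aim 1, Part B (trial of 26H vs 12HR) and Part C (MMT, vs. no MAT), patients will be seen monthly". The liver rule reads "Anyone whose LFTs increase to $>5X$ ULN, or $>3X$ ULN with symptoms of jaundice, nausea or fatigue, will be stopped from receiving medications". The neuropathy rule reads "if patients develop Grade 3 or higher peripheral neuropathy, they will be discontinued".

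**Drug-risk text (Section V, item 9).** For isoniazid above five times ULN, "discontinuation of INH should be strongly considered". The same paragraph also calls for prompt stopping on symptoms or signs of liver damage, with no enzyme threshold. For rifapentine, the text gives the same 5-times and 3-times-with-symptoms thresholds as item 10. In a separate paragraph it says that an isolated moderate rise "is not an indication to interrupt rifapentine therapy", and that the decision should follow repeat testing.

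**Use of the outcome.** Item 11 says of Part B: "Tolerability (discontinuation from study medication) will be the primary outcome". It would stop the study if the discontinuation rate is three times higher in either group. Item 12 compares the proportions completing therapy and models time to discontinuation by Cox regression.

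**The concern.** A participant can come off study drug because a rule requires it. When discontinuation is the outcome, that rule is part of the endpoint definition. Here there are two rules, and they do not give the same answer for the same participant. Staff working from item 3 would continue drug in some participants whom item 10 takes off it.

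Two things are at stake. The first is participant protection: the stated aim of Part B is to establish safety in prisoners with a high prevalence of HCV, and the individual stopping rule is ambiguous. The second is interpretation: the discontinuation rate, the 3-fold trigger, the completion proportion and the Cox analysis all depend on which text was followed, and the plan provides no way to tell afterwards.

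**Working it through.** The core check compares texts. Applying each rule to the same participant gives:

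| Situation | Item 3 | Item 10 |
|---|---|---|
| Grade 3 peripheral neuropathy | no trigger | stop |
| Grade 4 peripheral neuropathy | stop | stop |
| Liver tests above 3 and up to 5 times ULN with a named symptom | stop only if this is Grade 4; no mapping given | stop |
| Liver tests above 5 times ULN | stop only if this is Grade 4; no mapping given | stop |
| Grade 4 toxicity of another kind | stop | silent |
| Refusal or pregnancy | stop | silent |

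The first row is a difference on the face of the text. The third and fourth rows use different scales, and the documents never say which ULN multiple is DAIDS Grade 4. The size of the liver gap therefore cannot be derived.

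The item 9 text adds a secondary ambiguity. Nausea with enzymes below 3 times ULN meets the prompt-stop wording for isoniazid but not item 10. Isoniazid above five times ULN is a matter for strong consideration in item 9 and a required stop in item 10.

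The plan gives no figure to reproduce on this point. The following is an illustration of leverage only. The inputs from item 12 are completion of 67.0% (26H) and 82.1% (12HR), 177 per arm and alpha 0.05. I take alpha as two-sided, which the plan does not state, and treat non-completion as discontinuation.

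- Discontinuation ratio = (1 − 0.670)/(1 − 0.821) = 0.330/0.179 = 1.84.
- Power = Φ[(|p2 − p1|√n − 1.96√(2p̄q̄)) / √(p1q1 + p2q2)], where q = 1 − p and p̄ is the mean of p1 and p2. This is Φ[(0.151 × √177 − 1.96 × 0.616)/0.607] = Φ(1.32) = 0.907.

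Now assume that the broader of two rules also stops a fraction e of would-be completers, equally in both arms. The values of e are my assumption.

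- e = 5%: completion is 0.670 × 0.95 = 0.636 and 0.821 × 0.95 = 0.780; power 0.846, ratio 1.65.
- e = 10%: completion is 0.603 and 0.739; power 0.779, ratio 1.52.

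On these assumptions, even a rule applied evenly changes both the power and the distance to the 3-fold trigger. The finding does not rest on these figures.

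**The case against.** The best defence is that the lists are cumulative. Item 3 does not say that its triggers are the only ones, it answers a form question asking for a non-technical summary, and stopping someone under item 10 breaches nothing in item 3. That reading is possible, but neither item states it or points to the other. A reader of item 3 alone would not know that further mandatory triggers exist.

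Item 11 has the investigator and team review all discontinuations. This helps with those that occur. It does not reveal participants who stayed on drug under one text and would have been stopped under the other.

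Item 12 frames the comparison as completion rather than discontinuation, and qualifies completion as free of adverse side effects. Taken literally, a participant with Grade 3 neuropathy might count as a failure under either rule. That would shield the completion proportion, but not the item 11 outcome, the 3-fold trigger or the time-to-discontinuation analysis.

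A reader might infer that the two arms are under different stopping rules, because the rifapentine and isoniazid texts differ. The documents do not support this. The rifapentine text carries the same liver thresholds as item 10, its caution about isolated moderate rises is a separate remark, isoniazid is given in both arms, and item 10 applies to anyone in Part B. The contrast between a required stop in item 10 and a discretionary one in item 9 is also weak evidence by itself, because item 9 is general drug-risk background.

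**Conclusion.** The inconsistency is real. Two mandatory rules for stopping drug in an individual cover the same trial and differ outright at Grade 3 neuropathy. They use scales for the liver that the documents do not connect, and no precedence is given. The item 9 wording is a lesser ambiguity.

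The number of participants affected cannot be calculated. A reader might multiply the 21% isoniazid hepatotoxicity in item 12 by the HCV antibody prevalence of 63% to 94% in item 3: 0.21 × 0.63 = 13.2%, or 23 of 177, and 0.21 × 0.94 = 19.7%, or 35 of 177. That product does not measure this problem. The 21% has no stated threshold, cases on which both rules agree cause no conflict, and the upper figure needs an arm made up entirely of HIV-positive participants. Nor should it be set against a sized difference of 15 to 20 points: item 12 states 20%, and the roughly 15-point gap is the earlier trial's result.

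The conclusion assumes only that items 3 and 10 both govern Part B, which item 10 says in terms.

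**What to change.** Reconcile items 3 and 10 of Section V into one drug-discontinuation rule, stated once, cross-referenced elsewhere and applied identically in both arms. Align the isoniazid and rifapentine wording in item 9 with it, or mark that text as background that does not govern conduct. The clinical team decides the thresholds and whether the present lists are meant to be cumulative; no threshold is proposed here.

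Record on the case report form which criterion triggered each discontinuation, so that discontinuations required by the rule can be separated from refusals in the analysis and in reports to the monitoring board. If Part B participants have already been treated, document which text was followed and from what date.

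The cost is a wording amendment, one case report form field and a short note to site staff. Sample size and visit schedule are unaffected.
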